4.3 Patient Screening

This study can fulfill its objectives only if appropriate patients are enrolled. The following eligibility criteria are designed to select patients for whom protocol treatment is considered appropriate. All relevant medical and non-medical conditions should be taken into consideration when deciding whether this protocol is suitable for a particular individual. Patient eligibility will be reviewed and confirmed by the medical monitor or designee prior to randomization. Screening assessments (see the Schedule of Assessments [[Section 3.4](#)]) for this study must be performed between Day -28 and Day -1.

4.4 Inclusion Criteria

Patients who meet the following criteria will be considered eligible to participate in this clinical study:

1. Men and women, ages 18 to 70 years, inclusive
2. Patients must be mentally capable of giving consent and there must be evidence of a personally signed and dated informed consent document indicating that the patient has been informed of all pertinent aspects of the study
3. Patients must have SLE as defined by meeting 4 of the Systemic Lupus International Collaborating Clinics (SLICC) classification criteria for SLE (with at least 1 clinical and 1

immunologic criterion or Lupus nephritis as the sole clinical criterion in the presence of ANA or anti-dsDNA antibodies), either sequentially or simultaneously

4. At screening, patients must have at least 1 of the following:
 - a. Elevated ANA \geq 1:80 via immunofluorescent assay at the central laboratory
 - b. Positive anti-dsDNA or anti-Smith (Sm) above the normal level as determined by the central laboratory
 - c. C3 or C4 levels below normal as determined by central lab
5. At screening, the SLE Disease Activity Index 2000 (SLEDAI-2K) must be \geq 6, including points from at least 1 of the following clinical components:
 - a. Arthritis, rash, myositis, mucosal ulcers, pleurisy, pericarditis, and vasculitis
 - i. Excluding parameters which require central laboratory results: hematuria, pyuria, urinary casts, proteinuria, positive anti-dsDNA, decreased complement, thrombocytopenia, and leukopenia
 - ii. Points from lupus headache and organic brain syndrome will also be excluded
6. On Day 0, the SLEDAI-2K must be \geq 6, including points from at least 1 of the following clinical components:
 - a. Arthritis, rash, myositis, mucosal ulcers, pleurisy, pericarditis, and vasculitis
 - i. Excluding parameters which require central laboratory results: hematuria, pyuria, urinary casts, proteinuria, positive anti-dsDNA, decreased complement, thrombocytopenia, and leukopenia
 - ii. Points from lupus headache and organic brain syndrome will also be excluded
7. Patients must have at least 1A or 2Bs from the following manifestations of SLE, as defined by the BILAG criteria as modified for use in this study, which must be confirmed by the central data reviewer:
 - a. BILAG A or B score in the mucocutaneous body system
 - b. BILAG A or B score in the musculoskeletal body system due to active polyarthritis defined as follows:
 - i. “BILAG A:” Severe Arthritis, (BILAG item number 41), manifested by observed active synovitis in \geq 2 joints with marked loss of functional range of movements and significant impairment of basic activities of daily living that has been present on several days cumulatively over the past 30 days, including at the time of the screening visit. See [APPENDIX 5](#) for additional detailed specifications.
 - Basic ADLs are defined as the following activities which require assistance or assistive devices, (at least 1 must be present and documented in source):

- Ambulation, toileting, grooming- including bathing and dressing; feeding oneself
- ii. “BILAG B:” Moderate Arthritis, Tendonitis or Tenosynovitis, (BILAG item number 42), defined as tendonitis/tenosynovitis, or active synovitis in ≥ 1 joint, (observed or throughout history), with some loss of functional range of movements manifested by effects on instrumental ADLs such as:
 - Cooking, driving, using the telephone or computer, shopping, cleaning, etc., and has been present on several days over the last 30 days, and is present at the time of the screening visit

If only one “B” and no “A” score is present in the mucocutaneous body system or in the musculoskeletal body system due to arthritis, then at least 1 “B” must be present in the other body systems for a total of 2 “B” BILAG body system scores

8. Patients must be currently receiving at least 1 of the following:
 - a. Administration for a minimum of 12 weeks, and a stable dose for at least 56 days (8 weeks prior to signing consent) of the following permitted steroid-sparing agents:
 - i. Azathioprine (AZA), mycophenolate mofetil or mycophenolic acid, chloroquine, hydroxychloroquine, or methotrexate (MTX)
 - b. Prednisone (or prednisone-equivalent) cannot exceed 30 mg/day at screening for a patient to be eligible and must be stable at a maximum of 10 mg/day for at least 5 days prior to Day 0 (randomization) (see [APPENDIX 3](#))
9. Women of childbearing potential (WOCBP; see [Section 4.7](#) for full information regarding WOCBP, definition of menopause, and contraception):
 - a. Must have a negative serum pregnancy test at screening. Urine pregnancy test must be negative prior to first dose
 - b. Must not be breastfeeding
 - c. Must agree to follow instructions for method(s) of contraception for the duration of treatment with study drug plus 52 weeks
10. Men who are sexually active with WOCBP must agree to follow instructions for method(s) of contraception for the duration of treatment with study drug plus 52 weeks
11. Patients must demonstrate willingness and ability to comply with the scheduled study visits, treatment plans, laboratory tests, and other procedures

4.5 Exclusion Criteria

Patients presenting with any of the following will not be included in this study:

1. Drug-induced SLE, rather than “idiopathic” SLE

-
2. Other systemic autoimmune disease (eg, erosive arthritis, rheumatoid arthritis [RA], multiple sclerosis [MS], systemic sclerosis, or vasculitis not related to SLE)
 - a. RA-Lupus overlap (Rupus), and secondary Sjögren syndrome are allowed
 3. Any major surgery within 6 weeks of study drug administration, (Day 0), or any elective surgery planned during the course of the study
 4. Any history or risk for tuberculosis (TB), specifically those with:
 - a. Current clinical, radiographic, or laboratory evidence of active TB
 - b. History of active TB
 - c. Latent TB defined as positive QuantiFERON-TB Gold In-Tube (QFT-G) or other diagnostic test in the absence of clinical manifestations. Latent TB is not excluded if the patient has documented completion of adequate course of prophylactic treatment with regimen recommended by local health authority guideline, or the patient has started treatment with isoniazid, or other regimen recommended by local health authority guidelines for at least 1 month before Day 0 and continues to receive the prophylactic treatment during study until the treatment course is completed.
 5. Active or unstable lupus neuropsychiatric manifestations, including but not limited to any condition defined by BILAG A criteria, with the exception of mononeuritis multiplex and polyneuropathy, which are allowed
 6. Severe proliferative lupus nephritis, (WHO Class III, IV), which requires or may require induction treatment with cytotoxic agents or high dose CS
 7. Concomitant illness that, in the opinion of the investigator, is likely to require additional systemic glucocorticosteroid therapy during the study, (eg, asthma), is exclusionary
 - a. However, treatment for asthma with inhalational CS therapy is allowed
 8. Use or planned use of concomitant medication outside of standard of baseline treatment for SLE from Day -1 or for any time during the study. (See [Section 4.6](#) for prohibited concomitant medication)
 9. Active and clinically significant infection (bacterial, fungal, viral, or other) within 60 days prior to first dose of study drug. Clinically significant is defined as requiring systemic parenteral antibiotics or hospitalization
 10. A history of opportunistic infection, or a history of recurrent or severe disseminated herpes zoster or disseminated herpes simplex within the last 3 years
 11. Chronic viral hepatitis including hepatitis B (HBV) and hepatitis C (HCV) unless patient received curative treatment for HCV and has a documented negative viral load, known human immunodeficiency virus (HIV), or acquired immunodeficiency syndrome (AIDS)-related illness
 12. Cryptosporidium in the stool sample at screening
 13. White blood cells (WBC) $< 1,200/\text{mm}^3$ ($1.2 \times 10^9/\text{L}$) at screening
 14. Absolute neutrophil count (ANC) $< 500/\text{mm}^3$ at screening

-
15. CD4+ count < 350/ μ L at screening
 16. Platelets < 50,000/ mm^3 ($50 \times 10^9/\text{L}$) or < 35,000/ mm^3 ($35 \times 10^9/\text{L}$) if related to SLE, at screening
 17. Hemoglobin < 8 g/dL or < 7 g/dL at screening if related to SLE
 18. Proteinuria > 3.0 g/day (3000 mg/day) at screening or equivalent level of proteinuria as assessed by protein/creatinine ratio (3 mg/mg or 339 mg/mmol)
 19. Serum creatinine > 2.0 mg/dL at screening or creatinine clearance (CrCL) < 40 ml/minute based on Cockcroft-Gault calculation³⁹:

$$\text{GFR} = ([1 \text{ for male}] \text{ or } [0.85 \text{ for female}]) \times (140 - \text{Age}) \times \text{BW} / (72 \times \text{Creatinine})$$
 20. Serum ALT and/or serum AST > 2 \times ULN at screening, unless explicitly related to lupus based on the investigator's judgment
 21. Creatinine kinase (CK) > 3.0 \times ULN at screening, unless it is related to lupus myositis
 22. Direct bilirubin > 1.5 \times ULN at screening (unless related to Gilbert's syndrome)
 23. Any other laboratory test results that, in the opinion of the Investigator, might place a patient at unacceptable risk for participating in this study
 24. History of allergic or anaphylactic reaction to any therapeutic or diagnostic monoclonal antibody (eg, IgG protein) or molecules made of components of monoclonal antibodies
 25. History substance and/or alcohol abuse or dependence within the past 1 year, at the investigator's judgment
 26. History of cancer within the last 5 years (except for cutaneous basal cell or squamous cell cancer, or cervical cancer in situ resolved by excision)
 27. Any other severe acute or chronic medical or psychiatric condition, including recent (within the past year) medical conditions (eg, cardiovascular conditions, respiratory illnesses) that may increase the risk associated with study participation or investigational product administration or may interfere with the interpretation of study results and, in the judgment of the investigator, would make the patient inappropriate for entry into this study
 28. Investigational site staff members directly involved in the conduct of the trial and their family members, site staff members otherwise supervised by the investigator, or patients who are employees of the sponsor or directly involved in the conduct of the trial
 29. Currently participating in, or who have participated in other interventional (drug or device) clinical study within 30 days or 5 half-lives of baseline, whichever is longer
 30. Recent (within the past 12 months) or active suicidal ideation or behavior based on patient responding "yes" to question 3, 4 or 5 on the C-SSRS
 31. Current or pending incarceration

32. Current or pending compulsory detainment for treatment of either a psychiatric or physical (eg, infectious disease) illness

4.6 Concomitant Medications

Any medicinal product, prescribed or OTC, including herbal and other nontraditional remedies, is considered a concomitant medication. Patients should stay on stable regimen of other concomitant medications for the treatment of SLE (eg, analgesics, NSAIDs, statins, ACE inhibitors/ARBs and other antihypertensive drugs), unless changes in these treatments are clinically indicated. Use of any other drugs for non-SLE conditions, including over-the-counter medications and herbal preparations, should remain stable unless change or addition is clinically necessary. Discussion with the medical monitor prior to initiation of new medication is strongly recommended. Any concomitant therapies must be recorded on the eCRF. Prior and concomitant medication use will be recorded for the 30 days prior to screening until the last follow-up visit. In addition, historical treatment for SLE (including immunosuppressant, anti-malarial, corticosteroid, and/or biologic agent) will be recorded for the 48 weeks prior to screening in the eCRF.

4.6.1 Corticosteroid

Prior to randomization, oral CSs (prednisone or prednisone equivalent), may be used in accordance with the investigator's clinical judgment and best standard of care. See [APPENDIX 3](#) for examples of equivalents.

A maximum daily dose of 30 mg/day of oral CS will be acceptable for eligibility for the study, however, the daily dose must be tapered down to a maximum of 10 mg/day for at least 5 days prior to Day 0 (randomization day).

Tapering of steroids during the course of the study will be highly encouraged and should be evaluated at the protocol permitted visits (Day 0 through Day 60 and Day 120 through Day 150). Between Day 60 and Day 120, and between Day 150 and Day 210, oral CS doses must be held constant due to the endpoint evaluations occurring at Day 120 and Day 210.

- Once a patient has received the first dose of study drug (after Day 0), prednisone (or prednisone equivalent) dose is highly encouraged to continue tapering down as appropriate. The investigator should evaluate the prednisone dose at each visit and make the decision, within the protocol allowed windows.
 - Exception: Between Day 60 and Day 120, and between Day 150 and Day 210 (ie, within 60 days of primary and secondary endpoint assessments), oral CS doses must be held constant.

After Day 0 (first dose of study drug), a maximum of 1 oral CS “burst” for increased SLE disease activity will be allowed between Day 0 and Day 60, according to the following:

- The oral CS dose is allowed to increase to ≤ 40 mg/day of prednisone or equivalent, which must be tapered down to ≤ 10 mg/day within 2 weeks of initiation of the “burst”

- Alternatively, a single intramuscular (IM) dose of methylprednisolone (40 mg or equivalent) is permitted
- No increase of oral CS above baseline is permitted beyond Day 60

Treatment with inhalational CS therapy (eg, for asthma), or by any other route, but systemic administration, is allowed.

Treatment with intra-articular or intravenous CS is prohibited during the course of the study.

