4.6.2 Other Prohibited and/or Restricted Treatments

Prohibited and/or restricted medications taken prior to study drug administration and during the study are described below, and washout requirements are provided in [APPENDIX 4](#). Medications taken within 30 days prior to screening must be recorded on the eCRF.

1. Prior exposure to BOS161721
2. Patients who have received treatment with anti-CD20 monoclonal antibodies within 24 weeks of screening; recovery of B cells (CD19+) must be documented (record absolute number of CD19+ B cells)
3. Patients who have received treatment with cyclophosphamide within the 24 weeks prior to screening
4. Patients who have received treatment with cyclosporine (with exception of ophthalmic use), any other calcineurin inhibitor or other immunosuppressive medication not specified in the inclusion criteria within 4 weeks for oral use or 8 weeks for topical use of screening
5. Patients who are currently receiving or are scheduled to receive plasmapheresis or lymphapheresis therapy, or have received such therapy within 24 weeks prior to screening
6. Patients who have received any live vaccines within 30 days of screening. Note: Furthermore, live vaccines should not be used during the course of the study and within the 2 months following last dose. Other inactivated vaccines such as tetanus, etc., may be used according to local guidelines during treatment period
7. Patients who are scheduled or anticipated to have elective surgery during the course of the study
8. Initiation of new immunosuppressant or anti-malarial agent is not permitted. Note: Dose reduction or replacement may be allowed due to intolerability or shortage for patients on a stable dose prior to study initiation

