6.3.5 CLASI Response

The CLASI is a comprehensive tool for assessment of disease activity and damage in cutaneous lupus, shown to be valid, reliable, and sensitive to changes in disease activity.⁴⁸ Response is defined as 50% improvement from baseline in “A” or “B” scores. This assessment will be applied to all patients as all are required to have cutaneous disease activity.

For the secondary efficacy endpoint of CLASI response at Day 210, patient scores on MAD and POC studies will be compared with baseline for 50% improvement.

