APPENDIX 4 MEDICATION WASHOUT PERIODS

WASHOUT TIMES OF MEDICATIONS BASED ON 5 HALF-LIVES

Medication	Discontinuing Prior to Signing Consent
Abatacept (CTLA4Ig)	24 weeks
Alefacept	12 weeks
AMG 623 (blisibimod)	24 weeks
Anifrolumab	12 weeks
Atacicept (TACI-Ig)	12 weeks
Belimumab	24 weeks
Cyclophosphamide	24 weeks
Cyclosporine (except for CSA eye drops)	4 weeks for oral and 8 weeks for topical
Danazol	4 weeks
Dapsone	4 weeks
Eculizumab	12 weeks
Efalizumab	12 weeks
Epratuzumab	24 weeks
Intravenous globulin	4 weeks
Leflunomide	8 weeks (4 weeks for washout with cholestyramine)
Lenalidomide with cholestiramine	8 weeks
Lupuzor	12 weeks
Memantine	4 weeks
Natalizumab	24 weeks
Ocrelizumab	48 weeks (or 24 weeks with recovery of B cell)
Pimecrolimus	4 weeks
Plasmapheresis	24 weeks
Retinoids (oral or topical)	4 weeks
Rituximab	48 weeks (or 24 weeks with recovery of B cell)
Sirolimus	4 weeks
Tacrolimus	4 weeks
Thalidomide	8 weeks
Tocilizumab	12 weeks

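### Section 4.6.1 holds only oral corticosteroid constant before Day 120 and Day 210, so a clinically indicated new or increased local steroid on lupus skin can count towards the Day 210 CLASI response

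*Protocol*

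**What the plan says.** **The freeze.** Section 4.6.1 sets two windows, Days 60-120 and Days 150-210, in which "oral CS doses must be held constant due to the endpoint evaluations occurring at Day 120 and Day 210". A bullet in the same section describes these days as "within 60 days of primary and secondary endpoint assessments".

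**The permission.** Later in Section 4.6.1: "Treatment with inhalational CS therapy (eg, for asthma), or by any other route, but systemic administration, is allowed". Topical use falls within this on a plain reading, and intralesional use by inference. The next sentence prohibits intra-articular and intravenous CS for the whole study.

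**The endpoint.** Section 2.2 lists CLASI response among the Phase 2 secondary efficacy endpoints. Section 6.3.5 places it at Day 210, where "patient scores on MAD and POC studies will be compared with baseline for 50% improvement". It sets no condition on local treatment of the skin.

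**Nearby rules.** Section 4.6 asks for a stable regimen of other SLE medication, lifts this when a change is clinically indicated, and recommends talking to the medical monitor before a new drug is started. Section 4.6.2 limits calcineurin inhibitors and other unlisted immunosuppressives "within 4 weeks for oral use or 8 weeks for topical use of screening" and bars new immunosuppressants and anti-malarials. Appendix 4 sets a 4-week washout for "Retinoids (oral or topical)". None of these names topical CS.

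**The concern.** The freeze exists so that a steroid change does not drive the assessment that follows it. That reason applies to CLASI response as much as to SRI-4, since the section refers to primary and secondary assessments alike. Yet the rule names only the oral route, and the steroid most likely to change a skin score directly is the one applied to the skin.

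Take a patient whose rash flares at Day 180, who is prescribed a topical steroid because it is clinically indicated, and whose skin clears by Day 210. That patient can meet the 50% CLASI improvement without breaking any rule in the protocol. If the drug works on skin, placebo patients will have more active skin disease to treat locally, so the difference between arms would tend to shrink. At stake is the interpretability of one secondary endpoint in a proof-of-concept trial. That a local steroid can improve lesions enough to matter is clinical reasoning; the documents do not state it.

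**Working it through.** **Step 1: is local CS on lupus skin restricted anywhere?**

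| Text | Does it stop a new topical steroid at Day 180? |
|---|---|
| 4.6.1 freeze | No. Oral doses only. |
| 4.6.1 prohibited routes | No. Intra-articular and intravenous only. |
| 4.6 stable regimen | Not when a change is clinically indicated. |
| 4.6 medical monitor | No. Discussion is recommended, not required. |
| 4.6.2 item 8 | No. Immunosuppressants and anti-malarials; Section 4.6 lists corticosteroid as a separate class. |
| 4.6.2 item 4, Appendix 4 | No. Limits before screening or consent, on other agents. |
| 4.5 exclusion 8 | No. An entry criterion that refers to 4.6 for what is prohibited. |
| 8.2.3 medication failure | No. Triggered by prohibited medication or unallowable CS under 4.6, and written for the primary analysis. |

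The closest parallel is the intra-articular ban. That is also a local steroid, acting on joints that another secondary endpoint (the ACR-28 count) scores, and it is barred throughout. Skin has no counterpart rule.

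**Step 2: the plan's own figure.** Inputs from Section 8.1: 132 evaluable patients at 2:1, so 88 and 44; SRI-4 response 65% and 40%; two-sided 0.10; Pearson chi-squared. The normal approximation gives power 0.866 and exact enumeration gives 0.863. Both agree with the stated figure of more than 80%.

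**Step 3: weight of one patient.** If all 132 count for CLASI, one converted placebo patient adds 1/44 = 2.3 percentage points and one converted active patient 1/88 = 1.1. That denominator is uncertain. Section 6.3.5 says "all are required to have cutaneous disease activity", but inclusion 7 reads "Patients must have at least 1A or 2Bs from the following manifestations of SLE" and so also admits a musculoskeletal A alone. If 70% have skin disease (assumed), the denominators are 30.8 and 61.6, and the weights are 3.2 and 1.6 points.

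**Step 4: illustration only.** Assume CLASI rates equal the SRI-4 planning rates, and that local steroid turns a fraction c of non-responders into responders. Then p' = p + (1 - p)c, and with equal c the difference becomes (0.65 - 0.40)(1 - c). Power is by exact enumeration of the uncorrected Pearson test, 88 against 44, two-sided 0.10, counting rejections in favour of active.

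| c active / c placebo | Rates | Difference | Power |
|---|---|---|---|
| 0 / 0 | 65.0% v 40.0% | 25.0 points | 86% |
| 5% / 5% | 66.75% v 43.0% | 23.8 points | 83% |
| 10% / 10% | 68.5% v 46.0% | 22.5 points | 81% |
| 20% / 20% | 72.0% v 52.0% | 20.0 points | 74% |
| 5% / 10% | 66.75% v 46.0% | 20.8 points | 74% |

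At 5-10% equal conversion the loss is small. The 74% figures need either 20% conversion in both arms or an imbalance between arms, and nothing in the documents supports one value over another.

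**The case against.** The case against is substantial.

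- **Stability is the default.** Section 4.6 asks for a stable SLE regimen, the only example in the 4.6.1 permission is asthma, and the change log says text was added to deal with steroid use for non-SLE conditions. This stands in part: a new topical steroid on lupus skin relies on the clinical-indication exception. A reader might infer that the protocol invites free use of local CS before endpoints, and that goes too far. But a skin flare is a clinical indication, and the operative sentence carries no non-SLE limit.
- **Secondary-endpoint handling belongs to the SAP.** Section 8.2.4 says so, and Section 8 promises to assess the effects of background therapy use. For scoring this is fair, and an absent scoring rule is not the point made here. What sites may prescribe, however, is fixed in the protocol. Section 4.6 requires concomitant therapies to be recorded but does not name lesion site, without which a later rule could not reliably separate lupus skin from other use.
- **The topical-agent limits are not a parallel.** Correct. The 8-week and 4-week limits are washouts before screening or consent. A reader might take them as proof that topical treatment is controlled before endpoints, and they do not show that.
- **The effect is small and conservative.** Probably so. A reader might infer a false positive, or damage to SRI-4 or BICLA. The documents support neither: the expected direction is towards no difference, and no material effect on those composites is shown.

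**Conclusion.** The point holds as a gap between the stated reason for the freeze and its wording. Local CS newly started or increased on lupus skin in Days 150-210 is permitted when clinically indicated, and can contribute to a CLASI response at Day 210.

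The probable consequence is modest dilution of the treatment difference on that one secondary endpoint. Its direction assumes that the drug works on skin and that placebo patients therefore use more local steroid. Its size cannot be determined from the protocol, and the figures above rest wholly on assumed CLASI, conversion and skin-disease rates. The primary analysis and its stated power are not in question. This is a worthwhile, inexpensive improvement, and leaving it out would not undermine the trial.

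**What to change.** Keep the permission for non-systemic CS and add to Section 4.6.1:

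- Local CS applied to SLE skin lesions must be held constant between Day 60 and Day 120 and between Day 150 and Day 210 unless a change is medically necessary. Indication and site are recorded on the concomitant-medication eCRF.
- A medically necessary new start or increase in these windows counts as CLASI non-response at the assessment closing the window: the Day 210 secondary endpoint, and Day 120 if analysed.
- Such a start or increase is not a medication failure for the primary SRI-4 analysis.

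The wording should be must, not should, because Section 4.6 already has the softer form. A sensitivity table scoring these patients as non-responders for SRI-4 and BICLA is optional.

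Cost: a few sentences, two fields on an eCRF page already in use, and a few more CLASI non-responders in both arms. There are no added visits or procedures, and patients keep access to treatment for a flare. One limit remains: local CS started between Day 120 and Day 150 and then held constant is not counted, though the recorded dates will show it.
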